### **QT Prolonging Agents**

Any medications known to cause QT prolongation should be used with caution; periodic ECG and electrolyte monitoring should be considered.

### **Antiplatelet Agents and Anticoagulants**

Warfarin or vitamin K antagonists should not be administered concomitantly with ibrutinib. Supplements such as fish oil and vitamin E preparations should be avoided. Use ibrutinib with caution in subjects requiring other anticoagulants or medications that inhibit platelet function. Subjects with congenital bleeding diathesis have not been studied. For guidance on ibrutinib and the use of anticoagulants during procedures/surgeries see Section X.

Subjects requiring the initiation of therapeutic anticoagulation therapy (eg, atrial fibrillation), consider the risks and benefits of continuing ibrutinib treatment. If therapeutic anticoagulation is clinically indicated, treatment with ibrutinib should be held and not be restarted until the subject is clinically stable and has no signs of bleeding. Subjects should be observed closely for signs and symptoms of bleeding. No dose reduction is required when study drug is restarted.

### **Guidelines for Ibrutinib Management with Surgeries or Procedures**

Ibrutinib may increase risk of bleeding with invasive procedures or surgery. The following guidance should be applied to the use of ibrutinib in the perioperative period for subjects who require surgical intervention or an invasive procedure while receiving ibrutinib.

#### **Minor Surgical Procedures**

For minor procedures (such as a central line placement, needle biopsy, thoracentesis, or paracentesis) ibrutinib should be held for at least 3 days prior to the procedure and should not be restarted for at least 3 days after the procedure. For bone marrow biopsies that are performed while the subject is on ibrutinib, it is not necessary to hold ibrutinib for these procedures.

#### **Major Surgical Procedures**

For any surgery or invasive procedure requiring sutures or staples for closure, ibrutinib should be held at least 7 days prior to the intervention and should be held at least 7 days after the procedure and restarted at the discretion of the investigator when the surgical site is reasonably healed without serosanguineous drainage or the need for drainage tubes.

#### **Emergency Procedures**

For emergency procedures, ibrutinib should be held after the procedure until the surgical site is reasonably healed, for at least 7 days after the urgent surgical procedure.

15.2 **Lenalidomide for Oral Administration (Revlimid®)**

15.21 **Background:** Lenalidomide has antineoplastic, immunomodulatory and antiangiogenic characteristics via multiple mechanisms. Lenalidomide selectively inhibits secretion of proinflammatory cytokines (potent inhibitor of tumor necrosis factor-alpha secretion); enhances cell-mediated immunity by stimulating proliferation of anti-CD3 stimulated T cells (resulting in increased IL-2 and interferon gamma secretion); inhibits trophic signals to angiogenic factors in cells. Lenalidomide inhibits the growth of myeloma cells by inducing cell cycle arrest and cell death.

15.22 **Formulation and Dispensing:** Commercially available for oral administration as: Capsules: 5 mg, 10 mg, 15 mg and 25 mg  
Lenalidomide is approved for marketing only under a FDA approved, restricted distribution program called Revlimid REMS. Physicians, pharmacies, and patients must be registered; a maximum 28-day supply may be dispensed; a new prescription is required each time it is filled; pregnancy testing is required for females of childbearing potential.

15.23 **Preparation, storage, and stability:** Store oral capsules at controlled room temperature between 15°C and 30°C (59 °F and 86 °F). Refer to labeling on the bottle for expiration date of the commercial tablets.

15.24 **Administration:** Refer to the treatment section for specific administration instructions. Administer with water. Swallow capsule whole; do not break, open, or chew.

15.25 **Pharmacokinetic information:**  
**Absorption:** Rapid  
**Metabolism:** Approximately two-thirds of Lenalidomide is eliminated unchanged through urinary excretion.  
**Protein binding:** ~30%  
**Time to peak, plasma:** Healthy volunteers: 0.6-1.5 hours; Myeloma patients: 0.5-4 hours  
**Half-life elimination:** ~3 hours  
**Excretion:** Urine (~67% as unchanged drug)

15.26 **Potential Drug Interactions:**  
**Increased Effect/Toxicity:** Abatacept and Anakinra may increase the risk of serious infection when used in combination with Lenalidomide. Lenalidomide may increase the risk of infections associated with vaccines (live organism).  
**Decreased Effect:** Lenalidomide may decrease the effect of vaccines (dead organisms).  
**Herb/Nutraceutical Interactions:** Avoid echinacea (has immunostimulant properties; consider therapy modifications).

15.27 **Known potential adverse events:** Consult the package insert for the most current and complete information.

**Boxed Warnings:**

1. Potential for human birth defects
2. Hematologic toxicity (neutropenia and thrombocytopenia)
3. Deep Venous Thrombosis and Pulmonary Embolism

**Common known potential toxicities, >10%:**

Cardiovascular: Peripheral edema

Central nervous system: Fatigue, pyrexia, dizziness, headache

Dermatologic: Pruritus, rash, dry skin

Endocrine & metabolic: Hyperglycemia, hypokalemia

Gastrointestinal: Diarrhea, constipation, nausea, weight loss, dyspepsia, anorexia, taste perversion, abdominal pain

Genitourinary: Urinary tract infection

Hematologic: Thrombocytopenia, neutropenia, anemia, myelosuppression is dose-dependent and reversible with treatment interruption and/or dose reduction

Infection, especially when white blood cell count is low

Neuromuscular & skeletal: Muscle cramp, arthralgia, back pain, tremor, weakness, paresthesia, limb pain, muscle spasms

Ocular: Blurred vision

Respiratory: Nasopharyngitis, cough, dyspnea, pharyngitis, epistaxis, upper respiratory infection, pneumonia, shortness of breath

**Less common known potential toxicities, 1% - 10%:**

Cardiovascular: Edema, deep vein thrombosis, hypertension, chest pain, palpitation, atrial fibrillation, syncope

Central nervous system: Insomnia, hypoesthesia, pain, depression

Dermatologic: Brusing, cellulitis, erythema

Endocrine & metabolic: Hypothyroidism, hypomagnesemia, hypocalcemia

Gastrointestinal: Vomiting, xerostomia, loose stools

Genitourinary: Dysuria

Hematologic: Leukopenia, febrile neutropenia, Lymphopenia

Hepatic: ALT increased

Neuromuscular & skeletal: Myalgia, rigors, neuropathy

Respiratory: Sinusitis, rhinitis, bronchitis, pulmonary embolism

Miscellaneous: Night sweats, diaphoresis

**Rare known potential toxicities, <1% (Limited to important or life-threatening):**

Angioedema, Stevens-Johnson Syndrome and Toxic Epidermal Necrolysis

Tumor Lysis Syndrome, Graft vs. Host Disease, rhabdomyolysis, Kidney damage which may require dialysis

15.28 **Drug procurement:** As a requirement of the REMS program, access to Lenalidomide is restricted. Lenalidomide is approved for marketing only under a FDA approved, restricted distribution program called REVCLIMID REMS ([www.REVCLIMIDREMS.com](http://www.REVCLIMIDREMS.com)) formerly known as the RevAssist program. Physicians, pharmacies, and patients must be registered; a maximum 28-day supply may be dispensed; a new prescription is required each time it is filled; pregnancy testing is required for females of childbearing potential.

15.29 **Nursing Guidelines:**

- Myelosuppression is dose-dependent and reversible with treatment interruption and/or dose reduction. Monitor CBC w/diff regularly. Instruct patient to report any unusual bruising or bleeding (thrombocytopenia); signs and symptoms of infection (neutropenia); and energy conserving lifestyle (anemia).
- Lenalidomide can have thrombotic adverse events (i.e DVT and PE). Instruct patient to report any limb swelling or pain, and to seek medical attention for shortness of breath or chest pain.
- Because of the potential for birth defects patients should be instructed in effective methods of birth control. Female patients should use 2 forms of birth control during treatment and for 4 weeks after discontinuing therapy. Males must be instructed to use a latex condom during any sexual contact with a woman of child bearing potential (even if they have had a vasectomy), because it is unknown if lenalidomide is present in semen.
- Patients may experience pruritus, rash and dry skin. Because of the rare risk of Steven's Johnson Syndrome, patients should immediately report any rash to their provider.
- Drug may cause hyperglycemia. Patients with diabetes or impaired fasting glucose may need to have their glucose levels monitored more closely.
- Gastrointestinal side effects (diarrhea, constipation, nausea, dyspepsia, anorexia, etc) are commonly seen. Manage patient symptomatically and monitor for effectiveness.
- Patients may experience myalgias, arthralgias, parasthesias, and other generalized pain. Administer analgesics as ordered and monitor for their effectiveness. Rarely infective bursitis and arthritis have been reported. Instruct patients to report any joint pain or redness to study immediately.
- Upper respiratory symptoms (nasopharyngitis, cough, epistaxis, etc.) can be seen. Manage symptomatically and monitor for effectiveness.
- Agent may cause fatigue, dizziness, vertigo or blurred vision. Instruct patient to report abdominal pain and/or jaundice to the study team.
- All prescribers and patients must be enrolled into the REVOLIMID REMS program. Only enough lenalidomide for one cycle of therapy will be supplied to the patient each cycle.
- Rarely secondary malignancies have been seen after lenalidomide therapy, including MDS, squamous/basal cell carcinomas of the skin, T-cell type acute leukemia.
- Monitor Renal function, renal failure has been reported.

### 15.3 Dexamethasone for Oral Administration (DXM)

15.31 **Background:** Dexamethasone is an adrenal corticosteroid compound. Dexamethasone decreases inflammation by suppression of neutrophil migration, decreased production of inflammatory mediators, and reversal of increased capillary permeability; suppresses normal immune response. Dexamethasone's mechanism of antiemetic activity is unknown.

15.32 **Formulation:** Commercially available for oral administration as:  
Tablets [scored]: 0.5 mg, 0.75 mg, 1 mg, 1.5 mg, 2 mg, 4 mg, and 6 mg  
Solution, oral: 0.5 mg/mL (500 mL)  
Solution, oral concentrate: Dexamethasone Intensol: 1 mg/mL (30 mL)

15.33 **Preparation, storage, and stability:** Refer to package insert for complete preparation and dispensing instructions. Store oral tablets at room temperature between 20°C to 25°C (60°F to 77°F). Protect from moisture. Dispense in a well-closed, light-resistant container as defined in the USP/NF. Store oral liquid at room temperature, do not freeze. Do not use if solution contains a precipitate. Refer to commercial package for drug expiration date.

15.34 **Administration:** Refer to the treatment section for specific administration instructions. May be taken with meals to decrease GI upset.

15.35 **Pharmacokinetic information:**  
**Onset of action:** Prompt  
**Duration of metabolic effect:** 72 hours  
**Metabolism:** Hepatic  
**Half-life elimination:** Normal renal function: 1.8-3.5 hours; **Biological half-life:** 36-54 hours  
**Time to peak, serum:** Oral: 1-2 hours  
**Excretion:** Urine and feces

15.36 **Potential Drug Interactions:**  
**Cytochrome P450 Effect: Substrate** of CYP3A4 (major); **Induces** CYP2A6 (weak), 2B6 (weak), 2C8 (weak), 2C9 (weak), 3A4 (strong)  
**Increased Effect/Toxicity:** Aprepitant, azole antifungals, calcium channel blockers, cyclosporine, estrogens, and macrolides may increase the serum levels of corticosteroids. Corticosteroids may increase the hypokalemic effects of amphotericin B or potassium-wasting diuretics (loop or thiazide); monitor. Refer to the package insert for a listing of other drugs.  
**Decreased Effect:** Antacids and bile acid sequestrants may reduce the absorption of corticosteroids; may reduce the absorption of corticosteroids; separate administration by 2 hours. Aminoglutethimide, barbiturates, and CYP3A4 inducers may reduce the serum levels/effects of dexamethasone and dexamethasone may decrease the levels/effects of other CYP3A4 substrates. Serum concentrations of isoniazid may be decreased by corticosteroids. Corticosteroids may lead to a reduction in warfarin effect. Corticosteroids may suppress the response to vaccinations.  
**Ethanol/Nutrition/Herb Interactions:**  
Ethanol: Avoid ethanol (may enhance gastric mucosal irritation).  
Food: Dexamethasone interferes with calcium absorption. Limit caffeine.  
Herb/Nutraceutical: Avoid cat's claw, Echinacea (have immunostimulant properties)

15.37 **Known potential adverse events:** Consult the package insert for the most current and complete information.  
**Common known potential toxicities,** frequency not defined: Fluid and electrolyte disturbances, congestive heart failure in susceptible persons, hypertension, euphoria, personality changes, insomnia, exacerbation of infection, exacerbation or symptoms of diabetes, psychosis, muscle weakness, osteoporosis, vertebral compression fractures, pancreatitis, esophagitis, peptic ulcer, dermatologic disturbances,

convulsions, vertigo and headache, endocrine abnormalities, ophthalmic changes, and metabolic changes. Some patients have experienced itching and other allergic, anaphylactic or hypersensitivity reactions. Withdrawal from prolonged therapy may result in symptoms including fever, myalgia and arthralgia.

15.38 **Drug procurement:** Commercial supplies. Pharmacies or clinics shall obtain supplies from normal commercial supply chain or wholesaler.

15.39 **Nursing Guidelines:**

- Monitor regularly for hypertension, CHF and other evidence of fluid retention.
- Advise patient of possible mood or behavioral changes, i.e., depression, euphoria, insomnia, even psychosis. Instruct patient to report any suspected changes to healthcare team.
- Assess for symptoms of gastric ulcer, heartburn, or gastritis. Suggest antacids. Instruct patient to report symptoms to healthcare team if unable to control.
- Evaluate signs of infection, particularly local candidal infections and treat appropriately.
- Monitor blood glucose frequently.
- Instruct patient to report frequent, unrelenting headaches or visual changes to healthcare team.
- Advise patient that easy bruising is a side effect.

## 16.0 Statistical Considerations and Methodology

### 16.1 Overview

This is a phase I/II study of a novel regimen of Ibrutinib, dexamethasone, and lenalidomide in patients with MM. The phase I portion is designed to determine the maximum tolerated dose (MTD) of ibrutinib that can be combined with lenalidomide and dexamethasone in patients with relapsed MM. The phase II portion is designed to assess the confirmed response rate of Ibrutinib, dexamethasone, and lenalidomide using a one stage phase II study design with an interim analysis in patients with transplant ineligible newly diagnosed MM.

Note: Phase II will not be initiated until after FDA review of Phase I data and approval to continue.

16.11 Primary Endpoint: The primary endpoint of the phase I portion of this trial is to assess the maximum tolerated dose (MTD). The primary endpoint of the phase II portion of this trial is the rate of confirmed response. A confirmed response is defined as a patient who has achieved an sCR, CR, VGPR, or PR on two consecutive evaluations at any time during treatment. Confirmed response will be evaluated using all cycles. All patients meeting the eligibility criteria, who have signed a consent form and have begun treatment will be evaluable for response, unless they are determined to be a major violation.

16.12 Sample Size: This phase I portion of this study is expected to require a minimum of 6 and a maximum of 24 evaluable patients. For the phase II portion, the one stage study design with an interim analysis to be used is fully described below.

A minimum of 15 and a maximum of 34 evaluable patients will be accrued total onto this phase II study unless undue toxicity is encountered. We anticipate accruing an additional 5 patients (2 phase I, 3 phase II) to account for ineligibility, cancellation, major treatment violation, or other reasons for a total of 63 patients overall.

16.13 Accrual Rate and Study Duration: The anticipated accrual rate is 2 evaluable multiple myeloma patients per month. At this rate, it will likely take about 3 months to enroll, treat, and evaluate each cohort of 3 patients in the dose escalation portion. We expect to evaluate a maximum of 4 dose levels, for a total duration of approximately 1.5 years in the dose escalation portion. The phase II patients are expected to accrue in the subsequent 1.5 years. The maximum total study duration is expected to be approximately 3.5 years, or until the last patient accrued has been observed for at least 6 months.

16.2 Phase I Portion Study Design:

This portion of the study will consist of a phase I trial to determine the MTD of ibrutinib in combination with lenalidomide and dexamethasone. A standard cohort of 3 phase I design will be utilized as described below. Three patients will be treated at each dose level and observed for a minimum of four weeks (i.e. one full cycle) before new patients are treated. Doses will not be escalated in any individual patient.

16.21 MTD Definition: MTD is defined as the dose level below the lowest dose that induces dose-limiting toxicity (DLT) in at least one-third of patients (at least 2 of a maximum of 6 new patients). A total of 6 patients treated at the MTD will be sufficient to identify common toxicities at the MTD. For instance, those toxicities with an incidence of at least 25% will be observed with a probability of at least 82%  $(1-(1-0.25)^6)$ .

Refer to section 7.32 for determination of dose-limiting toxicity (DLT)

16.22 Dose Escalation: The dose escalation portion of this study will utilize a standard cohort of three design. The dose levels to which patients will be assigned in sequential cohorts are described in Section 7.3. The first cohort of three patients will be treated at dose level 1. Decisions on when and how to dose escalate are described below.

16.221 Three patients will be treated at a given dose level combination and observed for 1 cycle to assess toxicity.

16.222 If DLT is not seen in any of the 3 patients, 3 new patients will be accrued and treated at the next higher dose level. If DLT is seen in 2 or 3 of 3 patients treated at a given dose level, then the next 3 patients will be treated at the next lower dose level, if only 3 patients were enrolled and treated at this lower dose level.

16.223 If DLT is seen in 1 of 3 patients treated at a given dose level, up to 3 additional patients will be enrolled and treated at the same dose level. If DLT is seen in at least one of these additional three patients ( $\geq 2$  of 6), the MTD will have been exceeded and further accrual will cease to

this cohort. If dose-limiting toxicity (DLT) is not seen in any of the three additional patients, 3 new patients will be accrued and treated at the next higher dose level.

16.224 After enrolling 6 patients on a specific dose level, if DLT is observed in at least 2 of 6 patients, then the MTD will have been exceeded and defined as the previous dose unless only 3 patients were treated at the lower dose level. In that case, 3 additional patients will be treated at this lower dose level such that a total of 6 patients are treated at the MTD to more fully assess the toxicities associated with the MTD.

16.225 Dose de-escalation: If dose-limiting toxicity meets the stopping boundaries set by the above dose escalation algorithm at dose level 1 (for example, more than 1 out of 3 patients or more than 1 out of 6 patients), the next cohort of three patients will be entered at a dose level of -1. Further dose re-escalation will depend on the toxicity profile observed at these dose levels, and re-evaluation of the regimen by the study team may be done.

16.226 If a patient fails to complete the first cycle of treatment for reasons other than toxicity, the patient will be regarded as inevaluable and will be replaced.

16.227 Operating Characteristics for standard cohort of 3 design: The following table gives the probability of dose escalation at a single dose level as a function of the true probability of DLT at that level using the cohorts of 3 design described above.

True Rate of DLT (%)	Probability of Dose Escalation
10	0.91
20	0.71
30	0.49
40	0.31
50	0.17

16.23 Analysis Plans: All the relevant results pertaining to toxicity, MTD, response, timed endpoints and laboratory correlates will be examined in an exploratory and hypothesis-generating fashion. The small sample size and the heterogeneous patient population associated with phase I studies restricts the generalizability of the results. Any notable statistical result should only be viewed as preliminary evidence for further study in Phase II trials rather than a definitive finding in and of itself.

#### 16.231 Adverse Event Profile

The number and severity of all adverse events (overall and by dose-level) will be tabulated and summarized in this patient population. The Grade 3+ adverse events will also be described and summarized in a similar

fashion. This will provide an indication of the level of tolerance for this treatment combination in this patient group.

#### 16.232 Toxicity Profile

The term toxicity is defined as adverse events that are classified as either possibly, probably, or definitely related to study treatment. Non-hematologic toxicities will be evaluated via the ordinal CTC standard toxicity grading. Hematologic toxicity measures of thrombocytopenia, neutropenia, and leukopenia will be assessed using continuous variables as the outcome measures (primarily nadir) as well as categorization via CTC standard toxicity grading.

Overall toxicity incidence as well as toxicity profiles by dose level and patient will be explored and summarized. Frequency distributions, graphical techniques and other descriptive measures will form the basis of these analyses.

#### 16.233 Response Profile

A response is defined to be a sCR, CR, VGPR, or PR noted as the objective status. Response will be evaluated using all cycles of treatment. All patients meeting the eligibility criteria who have signed a consent form and have begun treatment will be evaluable for response.

Responses will be summarized by simple descriptive summary statistics delineating depth of response as well as stable and progressive disease in this patient population

### 16.3 Phase II Statistical Design:

#### 16.31 Decision Rule:

In a previous study of lenalidomide and dexamethasone in patients with transplant ineligible newly diagnosed multiple myeloma, 1076 patients were treated and evaluated for response. The overall response rate in 541 patients treated with 18 cycles of lenalidomide and dexamethasone was 73%. In 535 patients who received continuous dosing of lenalidomide and dexamethasone until disease progression, the overall response rate was 75%. An increase in overall response rate for ibrutinib, dexamethasone, and lenalidomide would be of interest.

The largest success proportion where the proposed treatment regimen would be considered ineffective in this population is 65%, and the smallest success proportion that would warrant subsequent studies with the proposed regimen in this patient population is 85%. The following one-stage design with an interim analysis is based on a two-stage Simon optimum design and requires 34 evaluable patients to test the null hypothesis that the true success proportion in this patient population is at most 65%

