## 2.0 Goals

### 2.1 Primary Objective:

- 2.11 Phase 1: To determine the maximum tolerated dose (MTD) of ibrutinib that can be combined with lenalidomide and dexamethasone in relapsed MM patients.
- 2.12 Phase 2: To estimate the overall response rate (ORR) including partial response (PR) or better of the combination of ibrutinib, lenalidomide, and dexamethasone in subjects with newly diagnosed MM who are not candidates for high dose chemotherapy and ASCT.

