#### 16.311 Interim Analysis: Enter 15 evaluable patients into the study. If 10 or fewer successes are observed in the first 15 evaluable patients, we will consider this regimen ineffective in this patient population and terminate the study. Otherwise, if the number of successes is at least 11, we will continue accrual.

16.312 Final Decision Rule: Enter an additional 19 evaluable patients into the study. If 25 or fewer successes are observed in the first 34 evaluable patients, we will consider this regimen ineffective in this patient population and terminate this study. Otherwise, if the number of successes is at least 26, this will be considered evidence of promising activity and the treatment may be recommended for further testing in subsequent studies in this population.

16.313 Over Accrual: If more than the target number of patients are accrued, the additional patients will not be used to evaluate the stopping rule or used in any decision making process.

16.314 NOTE: We will not suspend accrual at the interim analysis to allow the first 15 patients to become evaluable, unless undue toxicity is observed. Given the limited overall sample size and the inclusion of an adverse events stopping rule, we feel it is ethical to not halt accrual for the interim analysis. However, if accrual is extremely rapid, we may temporarily suspend accrual in order to obtain safety data on these patients before re-opening accrual to further patients.

16.32 Power and Significance Level: Assuming that the number of successes is binomially distributed, the significance level is .09, i.e. there is a 9% chance of finding the drug to be effective when it truly is not. The probability of declaring that this regimen warrants further study (i.e. statistical power) and the probability of stopping at the interim analysis under various success proportions can be tabulated as a function of the true success proportion as shown in the following table.

If the true success proportion is...	0.65	0.70	0.75	0.80	0.85
Then the probability of declaring that the regimen warrants further study is...	0.092	0.233	0.459	0.715	0.904
And the probability of stopping at the interim analysis is...	0.648	0.485	0.314	0.164	0.062

16.33 Other considerations: Adverse events, quality/duration of response, and patterns of treatment failure observed in this study, as well as scientific discoveries or changes in standard care will be taken into account in any decision to terminate the study.

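### The 9% error rate in 16.32 covers true response rates up to 65%, not a triplet that only matches the 73-75% cited for lenalidomide-dexamethasone; on that benchmark the rule would be met with probability 0.36-0.46

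*Combined protocol and SAP*

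**What the plan says.** The phase II part is a single-arm test on 34 evaluable patients with one interim look at 15.

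- **Benchmark (16.31).** From one earlier study in the same clinical setting: "The overall response rate in 541 patients treated with 18 cycles of lenalidomide and dexamethasone was 73" percent, and "In 535 patients who received continuous dosing of lenalidomide and dexamethasone until disease progression, the overall response rate was 75" percent. The section adds: "An increase in overall response rate for ibrutinib, dexamethasone, and lenalidomide would be of interest".
- **Null and target (16.31).** "The largest success proportion where the proposed treatment regimen would be considered ineffective in this population is 65" percent; the target is 85%. No reason is given for a null below the cited rates.
- **Decision rule (16.311, 16.312).** Stop if 10 or fewer of the first 15 respond. At the end, "if the number of successes is at least 26, this will be considered evidence of promising activity"; such a result permits, but does not require, a recommendation to study the regimen further in these patients.
- **Error rate (16.32).** The significance level is .09, explained as: "there is a 9% chance of finding the drug to be effective when it truly is not". The table below it gives the probability of declaring the regimen worth further study as 0.092, 0.233, 0.459, 0.715 and 0.904 at true rates of 0.65, 0.70, 0.75, 0.80 and 0.85.
- **Objective (2.12).** "To estimate the overall response rate (ORR) including partial response (PR) or better". A 95% confidence interval is planned in 16.412.

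**The concern.** Ibrutinib is the agent added to a known backbone, and there is no control arm. The only yardstick for what it adds is the pair of rates in 16.31. A reader who meets the explanation in 16.32 can easily take an ineffective drug to mean that ibrutinib adds nothing to lenalidomide-dexamethasone. On the cited figures that case sits at 73-75%, which is 8 to 10 points above the null, and the 9% does not apply there.

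The cut-off itself, 26/34 = 76.5%, lies only 1.5 points above the higher cited rate. What is at stake is how a positive result is read. A decision to take the triplet forward could rest on a 9% error figure when, on the plan's own benchmark, the chance of passing with no gain is several times larger.

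**Working it through.** **Inputs.** Interim: n = 15, continue at 11 or more (16.311). Final: n = 34, promising at 26 or more (16.312). Null 0.65 and target 0.85 (16.31). Cited backbone rates 0.73 and 0.75 (16.31).

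**Formulas.** For a true rate p:

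- P(promising) = sum over x = 11 to 15 of P(X = x) × P(Y ≥ 26 − x), with X ~ Bin(15, p) and Y ~ Bin(19, p).
- P(stop at interim) = P(X ≤ 10).

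**Step 1: reproduce the plan's figures.** At p = 0.65 the five terms are 0.0269 + 0.0329 + 0.0229 + 0.0084 + 0.0013 = 0.0924, which is the printed 0.092 and the stated .09. All ten values in the 16.32 table are reproduced to within 0.001.

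**Step 2: what the 9% bounds.** The null in 16.31 is a true rate of at most 65%. At 0.60 the probability is 0.029 and at 0.65 it is 0.092. It rises with p, so about 9% is the maximum error over the whole null. It says nothing about rates above 65%.

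**Step 3: the cited rates.** At p = 0.73 the terms are 0.0881 + 0.1212 + 0.0981 + 0.0438 + 0.0085 = 0.3597.

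| True rate | P(promising) | Ratio to 0.0924 | P(stop at interim) |
|---|---|---|---|
| 0.65 | 0.092 | 1.0 | 0.648 |
| 0.73 | 0.360 | 3.9 | 0.381 |
| 0.75 | 0.459 (as printed) | 5.0 | 0.314 |
| 0.85 | 0.904 | – | 0.062 |

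**Step 4: sensitivity.** Whether 73-75% applies to this endpoint is not known. If the backbone rate here were lower, P(promising) would be 0.138 at 67%, 0.166 at 68%, 0.233 at 70% and 0.314 at 72%. These are 1.5, 1.8, 2.5 and 3.4 times 0.0924.

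**Step 5: what a given count shows.** Exact (Clopper-Pearson) 95% intervals:

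| Successes of 34 | Observed | 95% interval | Excludes 73% and 75%? |
|---|---|---|---|
| 26 | 76.5% | 58.8-89.3% | No |
| 30 | 88.2% | 72.5-96.7% | No |
| 31 | 91.2% | 76.3-98.1% | Yes |

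Counts of 27 to 29 have lower limits of 62.1%, 65.5% and 68.9%, so they do not exclude the cited rates either. An exact interval that allows for the interim look gives 59.5-90.0% at 26 and lower limits of 72.6% at 30 and 76.3% at 31, so the change still falls at 31. The Duffy-Santner interval planned in 16.412 was not reproduced and may differ slightly.

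**The case against.** The case for the plan is strong on several points, and most of it stands.

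- **The 9% is correct on the plan's own terms.** Section 16.31 defines ineffective as a rate up to 65%, shortly before 16.32 uses the idea. A reader might infer that the figure is miscalculated, or that it holds at exactly 65% and nowhere else. Neither is so: it reproduces, and it bounds the error for every rate at or below 65%.
- **The upper figure is already disclosed.** The table prints 0.459 at 0.75. But the row is presented as power, the text does not connect it with the 75% in the preceding section, and 0.73 is not tabulated.
- **No superiority is claimed.** The objective is to estimate the response rate, and the rule leads only to a possible recommendation for further testing. A reader might infer that the plan promises a demonstrated gain over lenalidomide-dexamethasone; it does not. What is missing is a sentence that says so beside the benchmark, given that 16.31 names an increase as the thing of interest.
- **A null below a historical rate can be a legitimate choice.** With 65% and 85% as null and target, 75% is the midpoint, so a pass probability near one half there is expected. That explains the number. It does not supply the missing reason for 65%.
- **Carry-over is uncertain.** Success here needs two consecutive evaluations during treatment (16.11), lenalidomide is not given in cycle 1 (7.12), and permanently stopping ibrutinib or lenalidomide ends protocol therapy (8.1 d). These could lower the rate. Resetting the baseline after progression in cycle 1 (11.5) could raise it. Section 3.152 also admits fit patients for reasons such as preference or finances. So 0.36-0.46 should not be read as the trial's actual false-positive rate. The documents use none of these features to justify 65%.

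It would also go too far to say that no result of 26 or more could point to improvement: by the intervals above, 31 to 34 successes would exclude the cited rates.

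**Conclusion.** The point holds as one of interpretation, not of arithmetic. The significance level is right for true rates of 65% or lower, but its verbal explanation leaves out the comparison that 16.31 itself sets up. If the cited rates apply to this endpoint, a triplet that only matches them meets the rule with probability 0.36 (73%) to 0.46 (75%), about four to five times the stated 9%. At lower assumed backbone rates of 67-72% the probability is 0.14 to 0.31. Meeting the cut-off is evidence against 65% or less. At exactly 26 of 34 the result is compatible with no gain over lenalidomide-dexamethasone, and by exact intervals this remains so up to 30 of 34. The result rests on the binomial model, the stopping rule being applied as written and, for 0.36-0.46, the carry-over assumption.

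**What to change.** Three wording changes:

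1. **16.32.** Keep the binomial assumption and the .09. Replace the explanation that follows with: *i.e. there is at most about a 9% chance of declaring the regimen promising if the true success proportion is 65% or lower; if it equals the 73-75% cited in 16.31, this chance is 0.36-0.46.* Add a 0.73 column to the table: 0.360 for warranting further study and 0.381 for stopping at the interim.
2. **16.312.** Add: *Meeting the cut-off of 26 is evidence against a true success proportion of 65% or less; meeting it does not by itself show improvement over lenalidomide-dexamethasone, which is to be judged by whether the 95% confidence interval planned in 16.412 excludes the cited 73-75%.* The count at which this happens should be computed with the planned Duffy-Santner interval; by Clopper-Pearson it is 31 of 34.
3. **16.31.** State the reason for 65%, including any feature of the endpoint or population that is thought to make the cited rates too high for this trial.

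The sample size, interim rule and final cut-off do not change and no patients are added. The cost is a less favourable stated error rate.
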